Patient demographic characteristic data, such as birthweight and gestational age, and details of numbers and timing of recorded encounters (either examinations or treatments) in ROP Check® are analyzed for non-normal distribution by Shapiro Wilk test before non-parametric analysis.

Recently proposed alterations to the AAP screening guidelines have been published but until now, not yet compared with a North American cohort of premature infants with substantial numbers of infants of Pacific races that are at high risk for treatment-warranted ROP²⁻⁵ .

Compared study cohorts							ROP Check® from 2010 to 2022									
Study	Years	patients	BW>	GA>	1st exam?	miss ?	missed ?	Avoid ?	Cohort	Treat	%Tx	Tx GA		%ROP	Pacific	
E-ROP	2004-22	1257 of 6729	750	27	37 wk	1	4	2.0%	2975	32	1.1 %	33.6	41.6	80%	15%	
First-ROP	2017-23	1125 of 2004	800	27	34 wk	0	4	8.6%	2917	29	1.0 %	33.6	41.6	80%	47%	
Moir +	2003-22	6025 of 8364	1000	29	31-34 wk	0	4	3.1%	1543	4	0.3 %	36.1	37.9	90%	50%	
SCREEN-ROP	2016-24	61 of 823	1200	30	31-34 wk	0	2	"7.6%" "	625	2	0.3 %	37.5	37.7	94%	22%	
TWO-ROP	2013-23	1095 of 3239	1500	30	38-9 wk	0	3	2.2%	989	3	0.3 %	37.5	37.9	91%	21%	
ROP Check®										5058	387	7.7 %	29.1	47.7	59%	13%
"30+4"	2010-22	287 of 5058	any	30+4	31-34 wk	na	0	2.5%	287	0	0.0 %	na	na	93%	25%	

ROP-if-P	2010-22	957 of 5058	140	0	30	31-34 wk	na	0	7.90%	957	0	0.0 %	na	na	92%	0%
----------	---------	-------------	-----	---	----	----------	----	---	-------	-----	---	-------	----	----	-----	----

References:

1. Fierson WM, Ophthalmology AAOPSo, American Academy Of O, American Association For Pediatric O, Strabismus, American Association Of Certified O. Screening Examination of Premature Infants for Retinopathy of Prematurity. *Pediatrics*. Dec 2018;142(6):doi:10.1542/peds.2018-3061

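### The Pacific column of the comparison table has no stated denominator, and 13% overall cannot stand with 47% and 50% in two subsets; %ROP also needs a definition

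*Combined protocol and SAP*

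**What the plan says.** The combined protocol and SAP contains one table, which sets published screening proposals beside the ROP Check data. Its right-hand block is labelled as ROP Check data for 2010 to 2022 and carries the headings "Cohort Treat %Tx Tx GA %ROP Pacific". No text or footnote says what the last two columns are percentages of.

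The rows that matter most are:

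- Whole database: "5058 387 7.7 % 29.1 47.7 59% 13", so 13% Pacific among 5,058 infants.
- E-ROP: "2.0% 2975 32 1.1 % 33.6 41.6 80% 15", so 15%.
- First-ROP: "8.6% 2917 29 1.0 % 33.6 41.6 80% 47", so 47%.
- The rule with cut-offs BW>1000 and GA>29: "1543 4 0.3 % 36.1 37.9 90% 50", so 50%.
- SCREEN-ROP: "625 2 0.3 % 37.5 37.7 94% 22", so 22%.

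TWO-ROP prints 21%, the 30+4 row 25% and ROP-if-P 0%. The opening description makes comparison of screening criteria with this dataset an aim and describes the statistics as descriptive. The paragraph before the table presents the sizeable Pacific representation as what earlier comparisons lacked.

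**The concern.** Each rule's cohort is drawn from the same 5,058 infants, so no row can contain more Pacific infants than the total row. A total of 13% beside subsets at 47% and 50%, where the subsets make up 58% (2,917/5,058) and 31% (1,543/5,058) of the database, does not look possible. E-ROP and First-ROP also have almost the same cohort size (2,975 and 2,917) and similar cut-offs, yet the Pacific figure moves from 15% to 47%.

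Taken at face value, the table says that about half the infants covered by two competing proposals are Pacific, against 13% overall. In a descriptive study the percentages are the result, and this column bears on the feature said to distinguish the cohort.

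A second oddity is that %ROP rises from 59% overall to between 80% and 94% in the rule subsets, while the treated percentage falls from 7.7% to between 0% and 1.1%. That pattern suggests the column may hold the percentage without ROP.

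**Working it through.** **Inputs.** Cohort, Treat, %Tx, %ROP and Pacific, all from the comparison table. Each printed whole percentage is taken to be rounded to within 0.5 points.

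**Step 1: are the columns read correctly?** %Tx should equal Treat/Cohort:

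- E-ROP 32/2975 = 1.08% (printed 1.1%)
- First-ROP 29/2917 = 0.99% (1.0%)
- BW>1000/GA>29 4/1543 = 0.26% (0.3%)
- SCREEN-ROP 2/625 = 0.32% (0.3%)
- TWO-ROP 3/989 = 0.30% (0.3%)
- Total 387/5058 = 7.65% (7.7%)
- 30+4 and ROP-if-P: 0 treated (0.0%)

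All rows reproduce, so Cohort and Treat are in the right places.

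**Step 2: Pacific as a share of the cohort.** Whole-number counts that round to the printed percentage:

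| Row | Cohort | Printed | Pacific infants implied |
|---|---|---|---|
| Total | 5058 | 13% | 633–682 |
| E-ROP | 2975 | 15% | 432–461 |
| First-ROP | 2917 | 47% | 1357–1385 |
| BW>1000/GA>29 | 1543 | 50% | 764–779 |

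Both 1357 and 764 exceed 682, so each cell alone contradicts 13%. The smallest ratios are 1357/682 = 1.99 and 764/682 = 1.12.

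- If 13% is right, First-ROP can be at most 682/2917 = 23.4% and BW>1000/GA>29 at most 682/1543 = 44.2%.
- If 47% is right, the overall share is at least 1357/5058 = 26.8%.
- If 50% is right, the overall share is at least 764/5058 = 15.1%.

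**Step 3: Pacific as a share of treated infants.**

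- E-ROP, 15% of 32: 4/32 = 12.5% and 5/32 = 15.6%, so unattainable.
- First-ROP, 47% of 29: 13/29 = 44.8% and 14/29 = 48.3%, so unattainable.
- SCREEN-ROP, 22% of 2: only 0, 50 or 100% is possible.
- TWO-ROP, 21% of 3: only 0, 33, 67 or 100% is possible.
- 30+4: 25% printed with 0 treated. ROP-if-P also has 0 treated.

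Only two rows fit: 2/4 = 50%, and 49 to 52 of 387 = 13%.

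**Step 4: a conditional check.** The printed cut-offs are "1257 of 6729 750 27 37 wk" for E-ROP and "1125 of 2004 800 27 34 wk" for First-ROP. If the limits combine in the same way, First-ROP and BW>1000/GA>29 both lie inside E-ROP. The ceilings then fall to 461/2917 = 15.8% and 461/1543 = 29.9%. Nesting is not certain: TWO-ROP (BW>1500, GA>30) has 989 infants while SCREEN-ROP (BW>1200, GA>30) has 625, so counts do not always follow cut-offs. Steps 2 and 3 do not need nesting.

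**Step 5: %ROP as labelled.** Outside the E-ROP set there are 5058 − 2975 = 2083 infants.

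- Implied ROP there: (0.59 × 5058 − 0.80 × 2975)/2083 = 604/2083 = 29%. Rounding allows 565–643 infants, or 27–31%.
- Treated there: (387 − 32)/2083 = 355/2083 = 17.0%.
- If the column is instead the percentage without ROP: 20% with ROP inside E-ROP, and (0.41 × 5058 − 0.20 × 2975)/2083 = 1479/2083 = 71% outside.

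The second reading runs in the same direction as treatment. The first is arithmetically possible.

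**The case against.** The strongest reply is that a different denominator was meant. Pacific could be the share of all the database's Pacific infants who fall under each rule. With 633 to 682 such infants, 47% is about 298 to 321 and 50% about 317 to 341, both attainable. But the total row would then read 100%, not 13%, so this too requires a second denominator within the column.

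A share of infants with ROP as labelled fails: First-ROP needs about 0.47 × 0.80 × 2917 = 1,097, against 0.13 × 0.59 × 5058 = 388 overall. A share of the remaining infants gives about 274 (0.47 × 0.20 × 2917) against 270 (0.13 × 0.41 × 5058). Rounding leaves that open, and it is ruled out only if First-ROP is nested in E-ROP, where the same calculation gives 89 (0.15 × 0.20 × 2975). Nothing in the document suggests that this denominator was intended.

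A cell may also have been misplaced: 15/32 = 46.9%, so the First-ROP cell could be a treated share belonging to E-ROP. This is unproven, but it is a fair reminder that the 26.8% figure is conditional and is not an estimate of the true Pacific share.

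The table was damaged when its text was extracted, and a header line or footnote giving a denominator could have been lost. Step 1 validates only the counts and %Tx. That softens the complaint about a missing denominator, but lost text would not change the printed percentages.

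Finally, the %ROP point rests on a trend and not on a contradiction. That is correct, and it is why it remains a query.

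**Conclusion.** The concern holds. The three cells 13%, 47% and 50% cannot all be cohort shares, and the column cannot be a share of treated infants throughout. Either some cells are wrong or denominators were mixed; the documents do not show which, and the correct values cannot be derived from them. Read as cohort shares, the excess is at least 1.99-fold for First-ROP and 1.12-fold for BW>1000/GA>29. If 47% were the correct cell, the overall Pacific share would be about double the printed 13%.

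This rests on two assumptions: rounding to the nearest whole per cent, and every row being a subset of the 5,058. The block label supports the second, as do the last two rows, which give their counts out of 5,058. Confidence is high for the Pacific column and moderate for %ROP.

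The consequence is limited. No stated test or decision uses the column, and the treated counts, %Tx and the ROP-if-P row do not depend on the conflicting cells. It should still be corrected before the table is relied on, because description is the purpose of this study.

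**What to change.** Recompute Pacific in every row from a single race variable with a single stated denominator, print n/N beside each percentage, and correct the cells that change. The rule's cohort is the natural denominator, since %Tx already uses it. If a share among treated infants is also of interest, give it as a separate, labelled column.

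For %ROP, state the definition and denominator and check the source variable. Only if the sense is confirmed as reversed, relabel the column as the percentage without ROP or print the complement.

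The cost is one descriptive column recomputed from data already in hand, a line of table notes, and a check of one variable.
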